Study Protocol and Statistical Analysis Plan

B. SIGNIFICANCE:

B.1 Recurrent urinary tract infections in older women are common, poorly understood, and complicated by confounding symptom overlap.

Urinary tract infection (UTI) is the most common bacterial infection, accounting for more than 8 million office visits and 1 million emergency department visits each year in the United States.² Importantly, ~80% of visits for UTI are in women,³² and the highest rates of UTI recurrence occur in older women³³ who also have more variation and antibiotic resistance in the uropathogens that cause UTIs.^{5,34} It is clear that menopause is a predominant risk factor for rUTI and that the pathophysiology of a single, sporadic UTI in premenopausal women is very different than that of rUTI in older women.^{8,35} In older women with patient reported UTI, given the symptom overlap between overactive bladder and genitourinary syndrome of menopause, the diagnosis of acute UTI should be made using a combination of symptom assessment and urine diagnostic studies.^{14,36}

Although dysuria seems to be the most discriminating symptom for a culture-positive UTI,³⁷ we are still unable to reliably predict other factors that correlate with culture positivity and who will require antibiotics to clear a symptomatic UTI.³⁸ Prospective investigations are crucial to improve our ability to predict those that may have symptom resolution without antibiotic therapy, but also those that can be safely managed with a urine culture-directed antibiotic strategy.

B.2. Preliminary observational data suggests that a urine culture-directed antibiotic strategy for patient reported UTI in older women is safe, but randomized controlled trials are needed to substantiate broad adoption of such a strategy.

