Non-antibiotic treatment and placebo as initial management of UTI symptoms have been evaluated in several randomized controlled trials (RCTs) that enroll a mostly premenopausal population.^{16,39-43} An initial non-antibiotic strategy leads to a decrease in overall antibiotic use given either resolution of symptoms,¹⁸ or lack of bacteriuria.¹⁹ The results of these trials suggest that initial non-antibiotic management can be reasonable, but it may not be the method of choice for every woman with uncomplicated UTI. The literature on non-antibiotic treatment as initial management for UTI symptoms in older women is limited as the majority of studies did not enroll participants over the age of 65-70 and had a participant mean age of 30-40 years^{16,39-43} even though older women are an especially vulnerable population for drug interactions due to age-related physiologic changes and higher concomitant medication use.⁴⁴

Preliminary data: Recently, we performed a prospective cohort study on 152 women who were seeking care for UTI symptoms with mean age 66.4 (SD 14.9) of which 52.0% had a history of recurrent UTI. Women completed the UTI symptom assessment (UTISA) questionnaire⁴⁵ before they submitted a culture and then were either placed on empiric antibiotics or managed expectantly based on provider and/or patient preference. After urine cultures were resulted, participants completed another UTISA questionnaire and the global rating of change (GRC). Our primary outcome was “symptom improvement” defined as reporting symptoms of “better” on the GRC questionnaire.

Overall, 122 (80.3%) were managed expectantly, 30 (19.7%) were managed with empiric antibiotics.

The proportion of positive UCx in those treated empirically (53.3%) was similar to those managed expectantly (59%) (Table 1) which

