- Those with a negative urine culture will not be prescribed antibiotics and will be followed per protocol.
- Those with a positive urine culture who *report persistent UTI symptoms* will be given antibiotics following the priority list above with consideration to reported antimicrobial sensitivities.
- Those with a positive urine culture who *report resolution of UTI symptoms* will not be given antibiotic

Empiric Antibiotic Treatment.

- Those with a negative urine culture will be told to stop antibiotics
- Those with a positive urine culture sensitive to the empiric antibiotic will be instructed to complete the full course of their antibiotics
- Those with a positive culture resistant to empiric antibiotic will be given an alternative antibiotic per antibiotic protocol and will be followed per protocol. If there are no oral antibiotic options with patient-specific and antimicrobial sensitivities, we will engage local infectious disease physicians for management as per standard clinical protocols.

[figure not shown]
D.1.6. Study follow-up assessments.

All participants will be followed with electronic surveys via Research Electronic Data Capture (REDCap) software, which is a browser-based, metadata-directed EDC software and workflow methodology for designing

clinical and translational research databases,⁷² on day 2-3 (after result of urine culture). To avoid limiting enrollment to only those with access to technology, our research coordinator can also call and administer the questionnaire by phone to ensure ability to access and complete electronic materials. Follow-up assessments will be completed weekly for a total of 4 weeks. These will include UTISA questionnaire,⁶⁸ antibiotic associated side effects, use of other symptom mitigating remedies, and adherence to assigned study arm.

Participants will be provided with a clinical line to call 24/7 with report of worsening symptoms which will be discussed with the PI, [name] for determination of antibiotic prescription and if participants report fevers or chills this will prompt an in-person evaluation in clinic during business hours or the emergency department after hours. If participants call to report new symptoms during the study course, a repeat urine culture will be obtained.⁷³ Given that these episodes could be considered either a recurrent or incompletely treated infection we plan to manage these per clinical care and not based on the participants initial study arm.

Figure 2: Study Flow Diagram

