Analysis. All outcomes will be described using numbers and proportions of patients or means with confidence intervals. Proportions between groups will be compared with either chi-square or Fischer's exact testing and means will be compared with student's t-testing. Exploratory logistic regression modeling will be utilized to investigate the odds of both initial treatment failure and/or recurrent of UTI symptoms between groups and based on baseline characteristics

Power analysis:^{76,79} As above, we propose a future trial with a primary outcome to be symptom resolution at day 14 defined as 2 or less points (slight, very slight, or no problems) on all five components of the UTI symptom assessment (UTISA).^{43,78} The literature suggests 58-80% of women receiving empiric antibiotics for patient reported UTI will achieve clinical cure by day 3-7 after treatment initiation.^{43,78} Given that only women

with a positive urine culture will be given culture-directed antibiotics, and women in the empiric arm may have to have their antibiotics changed or stopped at the time of culture result, we anticipate a higher proportion of those in the culture-directed arm to have symptom resolution at day 7. Assuming 70% symptom resolution in the empiric arm, a future trial of 262 participants, with 131 per arm, would have 80% power to detect a 15-percentage point difference between groups with a 2-sided alpha of 0.05, while a sample size of 300 would be required assuming 65% resolution. Therefore, we believe that successfully recruiting a total of 70 participants at a rate of 6-7 participants/month will confirm the feasibility of future trial completion in <4 years (equivalent to other trials of antibiotic regimens for symptomatic UTI).^{17,78}

Statistical methods

Primary Outcomes	Statistical analysis
Feasibility: 
 - Number of subjects that were screened for participation - Number and proportion of subjects screened who met inclusion/exclusion criteria - Number and proportion of subjects who either declined participation or were ineligible (including reasons for ineligibility) - Number and proportion of eligible subjects that were enrolled in the study - Number and proportion of subjects enrolled who completed the study - Monthly enrollment rate 	Descriptive analysis = counts and proportions or means with standard deviation

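### The future trial is sized only at 70% and 65% control resolution, and the unconditional under-4-years conclusion does not hold across the plan's own figures

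*Combined protocol and SAP*

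**What the plan says.** All of the sizing is in the power analysis under the secondary exploratory aims of D.1.7 (combined protocol and SAP).

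- Source of the control rate, citing references 43 and 78 and referring to day 3-7 of treatment: "The literature suggests 58-80% of women receiving empiric antibiotics for patient reported UTI will achieve clinical cure".
- Base case: "Assuming 70% symptom resolution in the empiric arm", with "a future trial of 262 participants, with 131 per arm", for 80% power, a 15-point difference and two-sided alpha 0.05.
- Alternative: "while a sample size of 300 would be required assuming 65% resolution".
- Outcome: symptom resolution at day 14 on the UTISA. The culture-directed arm is expected to do better.
- Conclusion: recruiting 70 women at 6-7 a month confirms that the future trial can be completed in less than 4 years.

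Two background passages bear on the source of the range. B.2 says that trials of non-antibiotic or placebo management, a group cited as 16 and 39-43 and so including reference 43, "have been evaluated in several randomized controlled trials (RCTs) that enroll a mostly premenopausal population". It adds that most of them did not enrol beyond age 65-70 and had a mean age of 30-40. B.1 says that "the pathophysiology of a single, sporadic UTI in premenopausal women is very different than that of rUTI in older women". The population of reference 78 is not described anywhere.

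**The concern.** The duration statement links the pilot's recruitment target to the definitive trial, yet it carries no condition on control rate or accrual. The sizing covers the middle of the cited range and stops at 65%, although the range goes down to 58%. With a fixed 15-point gain, a lower control rate moves both proportions towards 50%, where their variance is larger and the difference is harder to detect.

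The range may also not describe the future control arm. At least one of its two sources belongs to a group of trials that the plan calls mostly premenopausal, and the range is for day 3-7 while the outcome is at day 14. At stake is whether meeting the pilot's recruitment target supports the feasibility conclusion that the plan attaches to it.

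**Working it through.** **Inputs** (power analysis, D.1.7): control rate 70% or 65%; range 58-80%; difference 15 points in favour of the culture-directed arm; two-sided alpha 0.05; power 80%; 1:1 allocation; 6-7 women a month; limit 48 months. No allowance for loss to follow-up is stated, so none is used.

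**Method.** Exact power is the sum, over all pairs (x, y) at which the test rejects, of Bin(x; n, p) × Bin(y; n, p + 0.15), where n is the number per arm and p the control rate. The rejection region is that of the two-sided Fisher exact test or of the uncorrected chi-square test.

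**Step 1: reproduce the plan's figures.**
- Fisher, 70 v 85%: 131 per arm gives 80.1% (130 gives 79.7%), so 262.
- Fisher, 65 v 80%: 150 per arm gives 80.3% (149 gives 79.9%), so 300.
- The uncorrected pooled formula gives 242 and 276, which do not match.

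The stated sizes are therefore Fisher sizes.

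**Step 2: duration on the plan's own sizes.**
- 262/6 = 43.7 months; 262/7 = 37.4 months.
- 300/6 = 50.0 months; 300/7 = 42.9 months.
- 300 women within 48 months need 300/48 = 6.25 a month.

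Of the four combinations, 65% at 6 a month breaks the limit.

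**Step 3: the low end of the cited range, 58 v 73%.**

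| | Fisher | Chi-square |
|---|---|---|
| Power with 262 | 68.3% | 72.6% |
| Power with 300 | 74.6% | 78.2% |
| Women for 80% power | 340 (170 per arm, 80.2%) | 312 (156 per arm, 80.1%) |
| Months at 7 a month | 340/7 = 48.6 | 312/7 = 44.6 |
| Months at 6 a month | 340/6 = 56.7 | 312/6 = 52.0 |

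**Step 4: where the 48-month limit falls (Fisher).**
- At 6 a month, 48 × 6 = 288 women (144 per arm). Power is 79.9% at a 66.5% control rate and 80.4% at 67%, so the limit is about 67%.
- At 7 a month, 48 × 7 = 336 women (168 per arm). Power is 79.85% at 58% and 80.2% at 58.5%, so the limit is about 58.5%.

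**Step 5: precision of the pilot's own control rate.** With about 35 women in the empiric arm and a true rate of 70%, the 95% margin is 1.96 × √(0.7 × 0.3/35) = 15.2 points, or about 55-85%. That is wider than 58-80%.

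**The case against.** The strongest reply is that this is an illustrative sizing of a later trial, and that it already includes a second scenario at 65%, below the 69% midpoint of the range ((58 + 80)/2). The arithmetic is right by Fisher's test. That stands, and it limits the weight of the point.

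Three stronger readings are tempting, and the documents do not support them.

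- *Older women with recurrent UTI resolve less often, so the trial is underpowered.* No figure in the documents shows this. B.2 describes a group of trials, using words for most of them, and does not describe reference 43 individually. Reference 78 is not described. Which source gave 58% and which 80% is unknown. A higher rate would raise power.
- *The plan itself says the rate does not carry over.* B.1 speaks of the pathophysiology of a sporadic infection, not of cure rates. The empiric-arm rule "Those with a negative urine culture will be told to stop antibiotics" (D.1.3.4) is not overlooked either: the power analysis mentions that antibiotics may be changed or stopped at the culture result.
- *At 58% the under-4-years claim fails whatever the accrual.* At 7 a month the Fisher overrun is 0.6 months, and by chi-square, which the Statistical methods table names for this outcome, 312 women take 44.6 months. At that accrual the result depends on the test. At 6 a month it exceeds 48 months by either test.

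It is also fair to say that 58% is a day 3-7 figure and so not a forecast for day 14. It serves here only as a sensitivity value from the range that the plan cites. Finally, chi-square would need 276 women at 65%, or 46.0 months at 6 a month; but the plan states 300, and 300 takes 50.

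**Conclusion.** The point holds as one about an unconditional claim. The under-4-years conclusion already fails at one of the plan's own combinations (300 women at 6 a month, 50 months). Extended to 58%, power with 262 women is 68% by Fisher (73% by chi-square), and 80% power needs 340 women (312 by chi-square). These figures assume a fixed 15-point gain, 1:1 allocation and no loss to follow-up; any allowance for loss would lengthen accrual. That 70% and 65% were drawn from the 58-80% range is inferred from the order of the sentences.

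How well the range describes day-14 resolution in women aged 65 or over with recurrent UTI cannot be settled from the documents, and neither can the direction of any difference. The pilot's outcomes and its sample of 70, which was set on resources, are unaffected. This is a point to consider, not a required change.

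**What to change.** In the future-trial power analysis of D.1.7:

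1. Name one test and give the size across the cited range by it. By Fisher: 262 at 70%, 300 at 65%, 340 at 58%.
2. Make the duration claim conditional. By Fisher, 48 months is enough for a control rate of about 67% or more at 6 a month, and about 58.5% or more at 7 a month.
3. State that the range comes at least partly from trials described as mostly premenopausal, and that it is for day 3-7 while the outcome is at day 14.
4. Say that the pilot's empiric-arm day-14 resolution, with its 95% CI, will be considered alongside the literature when the future control rate is set. It should not replace the literature, because about 35 women give a margin of about 15 points.

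The cost is a rewritten paragraph and one confidence interval from data already collected. The stated size and duration become less favourable. The pilot needs no extra participants.

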Preliminary data ([name] and [name], unpublished). We recently investigated the knowledge, attitudes, and management practices of primary care providers (PCP) when treating older women with symptoms attributed to UTI. Among 142 PCPs, the majority of which were female (60.6%) and practiced in a suburban location (50.7%), only 26.1% felt it was safe to wait for a urine culture before prescribing antibiotics, 62.0% felt delaying antibiotics depended on multiple factors, and 9.2% felt it was never safe to delay antibiotics. We found that 33.1% prescribe empiric antibiotics in ≥50% of encounters, 27.7% of providers were concerned over progression of symptoms and 49.5% of providers were concerned for progression to sepsis. A higher proportion of providers practicing >15 years always felt safe delaying antibiotics compared to those with ≤15 years of experience (33.3% v. 18.3%; p=0.04). **This cross-sectional survey found that providers with more clinical experience have more comfort delaying antibiotics in older women with UTI symptoms, but despite recent literature suggestive of an overall low risk of urosepsis in this population,²⁶ this sequela remains a significant concern among providers.**

This variability in antibiotic prescribing highlights the pressing need for level 1 evidence of the safety of a culture-directed approach to alleviate concerns among providers caring for older women. To update the current body of literature surrounding the natural progression of patient reported UTIs in ambulatory, community dwelling, older women, an initial randomized, feasibility trial of a urine culture-directed antibiotic approach in older women with patient reported UTI that includes standardized subjective and objective data is imperative. Data acquired from this pilot and feasibility study will provide us with important information regarding patient and provider willingness for enrollment, initial safety data and qualitative information that we can utilize to improve recruitment efficiency in a definitive trial.

B.7. Summary/Strengths of the current proposal:

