D.1.1 Overview and Design. The proposed pilot study is designed as a culture-directed versus empiric antibiotic strategy for patient-reported UTI symptoms in older women. (Figure 2) Over 12 months, we will recruit 70 women with rUTI. Following enrollment, patients will be randomized in a 1:1 ratio to one of two groups. Patients assigned to the culture-directed arm will await results of urine culture prior to potentially receiving antibiotics and those assigned to the empiric arm will be prescribed immediate antibiotics from an established list of commonly prescribed antibiotics. Participants will be sent electronic questionnaires after urine culture results and then weekly for a total of 4 weeks. The primary outcome is feasibility of trial defined as recruitment of 10% of eligible participants with 70% adherence to study protocol.

D.1.2 Recruitment and Subject Eligibility. Women age ≥65 years⁶¹ with diagnosis of recurrent UTI (rUTI) will be recruited from: 1) UPMC WCBPH faculty practices or 2) CTSI Pitt+Me® Research Registry. Eligibility criteria are listed in Table 2.

Rationale for Inclusion Criteria: We will include participants with patient reported recurrent UTI to allow for a pragmatic study design and generalizability. Additionally, our definition of patient reported UTI is like other RCTs evaluating non-antibiotic options as compared to antibiotic strategies for UTI treatment.^{43,62} We will exclude participants with features of complicated UTI in the setting of structural or functional abnormalities or instrumentation /catheterization^{4,63} Eligibility is limited to female biologic sex given the differential risk profile of males and females who experience recurrent UTIs.

D.1.3 Study procedures (Figure 2).

D.1.3.1 – Screening and Enrollment Procedures.

Information on the REDUCTION trial will be broadly disseminated in the University of Pittsburgh faculty practices at the WCBPH, through IRB approved brochures, social media ads, institutional (MWRI) and CTSI websites. Interested women will be encouraged to contact the research staff for more information. Women who meet eligibility criteria after screening will be provided a consent form via their preferred method (electronic or paper).

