
Pelvic floor distress inventory, PFDI-20; Urinary Tract Infection Symptom Assessment, UTISA
 * Adverse events will include either antibiotic related side effects, signs/symptoms of pyelonephritis and/or urosepsis or other serious adverse events

D.1.7. Data analysis.

Specific aim 1A) To evaluate the feasibility of recruiting eligible participants into a randomized trial of a culture-directed versus empiric antibiotic strategy for patient-reported UTI symptoms in older women.
 All outcomes for the feasibility assessment will be descriptive using numbers and proportions of patients and 95% CIs. We will report the number of patients assessed for eligibility along with the numbers excluded based on not meeting inclusion criteria, participation declined, and other reasons.⁷⁴ We will document number and proportion of enrolled participants who were randomized along with the number/proportion who received their

allocated assignment. We will document those lost-to follow-up including potential reasons. These data will provide information on the feasibility of recruiting patients into a future, large randomized, placebo controlled clinical trial. We believe that successfully recruiting 10% of eligible patients (e.g., 6-7 patients per month) will confirm the capacity to recruit for a future trial.

Power calculation:^{75,76} The primary outcome is feasibility which we will define as the ability to recruit 10% of eligible patients. As this is a pilot study, the sample size of 70 patients was determined based on clinical and logistical resources rather than statistical requirements for hypothesis testing. We anticipate screening approximately 1200 potentially eligible patients (based on known clinical data from our practice and current enrollment of women with recurrent UTI in Pitt+Me®) during the 12 months of recruitment (~100 per month) of which at least 800 will be deemed eligible and have UTI symptoms. (~67 per month) This is based on data from our group on urine cultures sent annually and time between UTI episodes.³⁵ A 95% confidence interval (CI) for the recruitment rate provides a 2.4% margin of error (MoE) assuming the true rate is 10%.

Specific aim 1B) To evaluate participant adherence to study procedures.

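### Completion in under 4 years does not follow for the 300-woman future trial at 6 per month (50 months); it holds for 262 at every quoted rate, and for 300 at the plan's own 10% criterion

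*Combined protocol and SAP*

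**What the plan says.** The Power analysis under the secondary exploratory aims (D.1.7) sizes the future trial twice. With 70% of the empiric arm resolving, "a future trial of 262 participants, with 131 per arm, would have 80% power to detect a 15-percentage point difference between groups". The sentence then adds "while a sample size of 300 would be required assuming 65% resolution". The next sentence opens with a 'Therefore' and concludes that "successfully recruiting a total of 70 participants at a rate of 6-7 participants/month will confirm the feasibility of future trial completion in <4 years". It does not limit this to one of the two sizes or to part of the rate range.

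The pilot's recruitment benchmark is expressed in three ways:

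- As a percentage. D.1.1 states: "The primary outcome is feasibility of trial defined as recruitment of 10% of eligible participants with 70% adherence to study protocol". The Power calculation under Specific aim 1A supplies the denominator, about 1200 women screened in 12 months, "of which at least 800 will be deemed eligible and have UTI symptoms. (~67 per month".
- As a monthly rate. Specific aim 1A states: "We believe that successfully recruiting 10% of eligible patients (e.g., 6-7 patients per month) will confirm the capacity to recruit for a future trial".
- As a total and a period. D.1.1 states: "Over 12 months, we will recruit 70 women with rUTI".

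**The concern.** The duration claim is simple division, so each size can be checked against each rate. One of the four corner combinations, 300 women at 6 per month, exceeds 48 months. The three expressions of the benchmark also imply different rates, and two of them admit rates at which the larger trial does not fit.

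Feasibility is the pilot's primary outcome, monthly enrolment is one of its listed measures, and this sentence carries the recruitment result over to the definitive trial. As worded, a pilot that enrolled 6 women per month could be reported as confirming completion in under 4 years for both sizes, when it would do so for only one.

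**Working it through.** **Inputs.** Sizes 262 and 300, rate 6–7 per month and limit of 4 years (48 months): Power analysis. Eligible women, 800 in 12 months or about 67 per month, and the 10% criterion: Specific aim 1A. Pilot target, 70 in 12 months: D.1.1. Follow-up per participant, 4 weeks: D.1.6. That is the pilot's follow-up. The future trial's total follow-up is not given, so 4 weeks is an assumption here.

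**Formulas.** Accrual months = size / monthly rate. Completion months = accrual + 28/30.4375 = accrual + 0.92.

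**Reproducing the plan's figure.** For 262: 262/7 = 37.4 and 262/6 = 43.7 months, both under 48. With follow-up, the slower case is 43.7 + 0.92 = 44.6. The claim reproduces for this size across the quoted range.

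**Rates implied by the three benchmarks.**

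- 10% of 800 = 80 women in 12 months; 80/12 = 6.67 per month.
- The lower figure of the quoted range: 6 × 12 = 72 women; 72/800 = 9.0%.
- 70 in 12 months: 70/12 = 5.83 per month; 70/800 = 8.75%.

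**Months for both sizes, before any loss.**

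| Rate per month | Share of 800 | 262, accrual | 262, with follow-up | 300, accrual | 300, with follow-up |
|---|---|---|---|---|---|
| 7 | 10.5% | 37.4 | 38.3 | 42.9 | 43.8 |
| 6.67 | 10.0% | 39.3 | 40.2 | 45.0 | 45.9 |
| 6.25 | 9.4% | 41.9 | 42.8 | 48.0 | 48.9 |
| 6 | 9.0% | 43.7 | 44.6 | 50.0 | 50.9 |
| 5.83 | 8.75% | 44.9 | 45.8 | 51.4 | 52.3 |

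**Break-even rates for 48 months.**

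- 262, accrual only: 262/48 = 5.46 per month. With follow-up: 262/47.08 = 5.56. Every rate in the table exceeds both.
- 300, accrual only: 300/48 = 6.25 per month. With follow-up: 300/47.08 = 6.37, about 6.4. The rates 7 and 6.67 exceed both; 6 and 5.83 exceed neither.

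**Overrun for 300.** At 6 per month: 50.0 − 48 = 2.0 months, or 2.9 with follow-up. At 5.83 per month: 51.4 − 48 = 3.4 months, or 4.3 with follow-up.

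**The case against.** The strongest reply is that the governing criterion is 10% of eligible women, and that 6–7 is a loose rounding of 10% of 67, introduced only as an example. At 6.67 per month both sizes fit, so only the rounded-down end of the range fails, for the alternative size, by about 2 months of accrual. This stands as a limit on how much the point matters. It does not clear the sentence: the Power analysis repeats 6–7 without the 10% and without the example wording, and 6 per month is below 10% of 800. A pilot that met its 12-month target exactly would also fall below that criterion.

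One could add that 300 is a sensitivity case. The plan nevertheless gives it as the size required at 65% resolution, and 65% lies inside the 58–80% cure range that the plan cites.

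The future trial might also recruit faster, since section B.3 expects "qualitative information that we can utilize to improve recruitment efficiency in a definitive trial". But no faster rate or additional site is given, and the duration is argued from the pilot's rate.

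Finally, a pilot of 70 cannot separate 6.0 from 6.25 per month. If accrual is Poisson (an assumption), 70 women in 70/6 = 11.67 months gives an exact 95% interval of about 4.7 to 7.6 per month. This is a fair reason not to make 6.25 a new pass mark. It leaves the arithmetic of the stated claim unchanged.

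Two stronger readings are tempting. A reader might infer that the definitive trial cannot finish in 4 years; the documents do not support this, because at their own 10% criterion even 300 women are accrued in 45 months. A reader might also infer that 262 fails once loss to follow-up is added. The plan gives no loss rate for a trial that it does not itself conduct, so that conclusion would rest on a figure supplied from outside.

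**Conclusion.** Wrong as written, and minor. For 300 women, under 4 years is not supported at 6 per month, nor at any rate up to 6.25 per month (about 6.4 with follow-up), nor at 70 women in 12 months. It is supported for 262 at every rate above, and for 300 at the 10% criterion.

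This rests on four assumptions: the future trial recruits at the pilot's rate, accrual is steady, no allowance is made for loss, and follow-up (where counted) is the pilot's 4 weeks. The rate of 6.67 also depends on the projected 800 eligible women being found. Ten per cent would fall to the accrual break-even of 6.25 per month at 6.25 × 12/0.10 = 750 eligible.

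Only the feasibility conclusion drawn for the future trial is affected. The pilot's size, conduct and analyses stay as they are.

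**What to change.** 1. In Specific aim 1A and in the Power analysis, replace 6–7 per month with the rate that the 10% criterion implies, about 6.7 per month. Under 4 years then holds for both sizes.
2. In the Power analysis, add a sentence such as: At 6 participants per month, or at 70 participants in 12 months, completion in under 4 years is supported for 262 participants only.
3. In the same place, state that these durations assume the future trial recruits at the pilot's rate.

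The cost is one figure in two places and two sentences. The 12-month target of 70 in D.1.1 can stay, because the added sentence says what it does and does not support.
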